Appendix C: FACIT Fatigue Scale

FACIT Fatigue Scale (Version 4)

Below is a list of statements that other people with your illness have said are important. Please circle or mark one number per line to indicate your response as it applies to the past 7 days.

		Not at all	A little bit	Some- what	Quite a bit	Very much
HI7	I feel fatigued	0	1	2	3	4
HI12	I feel weak all over	0	1	2	3	4
An1	I feel listless ("washed out")	0	1	2	3	4
An2	I feel tired	0	1	2	3	4
An3	I have trouble starting things because I am tired	0	1	2	3	4
An4	I have trouble finishing things because I am tired	0	1	2	3	4
An5	I have energy	0	1	2	3	4
An7	I am able to do my usual activities	0	1	2	3	4
An8	I need to sleep during the day	0	1	2	3	4
An12	I am too tired to eat	0	1	2	3	4
An14	I need help doing my usual activities	0	1	2	3	4
An15	I am frustrated by being too tired to do the things I want to do	0	1	2	3	4
An16	I have to limit my social activity because I am tired	0	1	2	3	4

English (Universal) Copyright 1987, 1997 16 November 2007 Page 1 of 1

Page 67 of 76

Appendix D: The Chronic Liver Disease Questionnaire (CLDQ)

The Chronic Liver Disease Questionnaire (CLDQ)

This questionnaire is designed to find out how you have been feeling during the last two weeks. You will be asked about your symptoms related to your liver disease, how you have been affected in doing activities, and how your mood has been. Please complete all of the questions and select only **one** response for each question.

1. How much of the time during the last two weeks have you been troubled by a feeling of abdominal bloating?

- 1 All of the time
- 2 Most of the time
- 3 A good bit of the time
- 4 Some of the time
- 5 A little of the time
- 6 Hardly any of the time
- 7 None of the time

2. How much of the time have you been tired or fatigued during the last two weeks?

- 1 All of the time
- 2 Most of the time
- 3 A good bit of the time
- 4 Some of the time
- 5 A little of the time
- 6 Hardly any of the time
- 7 None of the time

3. How much of the time during the last 2 weeks have you experienced bodily pain?

- 1 All of the time
- 2 Most of the time
- 3 A good bit of the time
- 4 Some of the time
- 5 A little of the time
- 6 Hardly any of the time
- 7 None of the time
- 4. How often during the last two weeks have you felt sleepy during the day?
- 1 All of the time
- 2 Most of the time
- 3 A good bit of the time
- 4 Some of the time
- 5 A little of the time
- 6 Hardly any of the time
- 7 None of the time

© Younossi 1997 Revised December 28, 1998

Page 68 of 76

- 5. How much of the time during the last two weeks have you experienced abdominal pain?
- 1 All of the time
- 2 Most of the time
- 3 A good bit of the time
- 4 Some of the time
- 5 A little of the time
- 6 Hardly any of the time
- 7 None of the time
- 6. How much of the time during the last two weeks has shortness of breath been a problem for you in your daily activities?
- 1 All of the time
- 2 Most of the time
- 3 A good bit of the time
- 4 Some of the time
- 5 A little of the time
- 6 Hardly any of the time
- 7 None of the time
- 7. How much of the time during the last two weeks have you not been able to eat as much as you would like?
- 1 All of the time
- 2 Most of the time
- 3 A good bit of the time
- 4 Some of the time
- 5 A little of the time
- 6 Hardly any of the time
- 7 None of the time
- 8. How much of the time in the last two weeks have you been bothered by having decreased strength?
- 1 All of the time
- 2 Most of the time
- 3 A good bit of the time
- 4 Some of the time
- 5 A little of the time
- 6 Hardly any of the time
- 7 None of the time

9. How often during last 2 weeks have you had trouble lifting or carrying heavy objects?

- 1 All of the time
- 2 Most of the time
- 3 A good bit of the time
- 4 Some of the time
- 5 A little of the time
- 6 Hardly any of the time
- 7 None of the time

© Younossi 1997 Revised December 28, 1998

Page 69 of 76

10. How often during the last two weeks have you felt anxious?

- 1 All of the time
- 2 Most of the time
- 3 A good bit of the time
- 4 Some of the time
- 5 A little of the time
- 6 Hardly any of the time
- 7 None of the time

11. How often during the last 2 weeks have you felt a decreased level of energy?

- 1 All of the time
- 2 Most of the time
- 3 A good bit of the time
- 4 Some of the time
- 5 A little of the time
- 6 Hardly any of the time
- 7 None of the time

12. How much of the time during the last two weeks have you felt unhappy?

- 1 All of the time
- 2 Most of the time
- 3 A good bit of the time
- 4 Some of the time
- 5 A little of the time
- 6 Hardly any of the time
- 7 None of the time

13. How often during the last two weeks have you felt drowsy?

- 1 All of the time
- 2 Most of the time
- 3 A good bit of the time
- 4 Some of the time
- 5 A little of the time
- 6 Hardly any of the time
- 7 None of the time

14. How much of the time during the last two weeks have you been bothered by a limitation of your diet?

- 1 All of the time
- 2 Most of the time
- 3 A good bit of the time
- 4 Some of the time
- 5 A little of the time
- 6 Hardly any of the time
- 7 None of the time

© Younossi 1997 Revised December 28, 1998

Page 70 of 76

15. How often during the last two weeks have you been irritable?

- 1 All of the time
- 2 Most of the time
- 3 A good bit of the time
- 4 Some of the time
- 5 A little of the time
- 6 Hardly any of the time
- 7 None of the time
- 16. How much of the time during the last two weeks have you had difficulty sleeping at night?
- 1 All of the time
- 2 Most of the time
- 3 A good bit of the time
- 4 Some of the time
- 5 A little of the time
- 6 Hardly any of the time
- 7 None of the time

17. How much of the time during the last two weeks have you been troubled by a feeling of abdominal discomfort?

- 1 All of the time
- 2 Most of the time
- 3 A good bit of the time
- 4 Some of the time
- 5 A little of the time
- 6 Hardly any of the time
- 7 None of the time

18. How much of the time during the last two weeks have you been worried about the impact your liver disease has on your family?

- 1 All of the time
- 2 Most of the time
- 3 A good bit of the time
- 4 Some of the time
- 5 A little of the time
- 6 Hardly any of the time
- 7 None of the time
- 19. How much of the time during the last two weeks have you had mood swings?
- 1 All of the time
- 2 Most of the time
- 3 A good bit of the time
- 4 Some of the time
- 5 A little of the time
- 6 Hardly any of the time
- 7 None of the time

© Younossi 1997 Revised December 28, 1998

Page 71 of 76
20. How much of the time during the last two weeks have you been unable to fall asleep at night?

- 1 All of the time
- 2 Most of the time
- 3 A good bit of the time
- 4 Some of the time
- 5 A little of the time
- 6 Hardly any of the time
- 7 None of the time

21. How often during the last two weeks have you had muscle cramps?

- 1 All of the time
- 2 Most of the time
- 3 A good bit of the time
- 4 Some of the time
- 5 A little of the time
- 6 Hardly any of the time
- 7 None of the time

22. How much of the time during the last two weeks have you been worried that your symptoms will develop into major problems?

- 1 All of the time
- 2 Most of the time
- 3 A good bit of the time
- 4 Some of the time
- 5 A little of the time
- 6 Hardly any of the time
- 7 None of the time

23. How much of the time during the last two weeks have you had a dry mouth?

- 1 All of the time
- 2 Most of the time
- 3 A good bit of the time
- 4 Some of the time
- 5 A little of the time
- 6 Hardly any of the time
- 7 None of the time

24. How much of the time during the last two weeks have you felt depressed?

- 1 All of the time
- 2 Most of the time
- 3 A good bit of the time
- 4 Some of the time
- 5 A little of the time
- 6 Hardly any of the time
- 7 None of the time

© Younossi 1997 Revised December 28, 1998

Page 72 of 76

ALEXION PHARMACEUTICALS, INC. PROPRIETARY AND CONFIDENTIAL: DO NOT COPY OR DISTRIBUTE WITHOUT PERMISSION

25. How much of the time during the last two weeks have you been worried about your condition getting worse?

- 1 All of the time
- 2 Most of the time
- 3 A good bit of the time
- 4 Some of the time
- 5 A little of the time
- 6 Hardly any of the time
- 7 None of the time

26. How much of the time during the last two weeks have you had problems concentrating?

- 1 All of the time
- 2 Most of the time
- 3 A good bit of the time
- 4 Some of the time
- 5 A little of the time
- 6 Hardly any of the time
- 7 None of the time

27. How much of the time have you been troubled by itching during the last two weeks?

- 1 All of the time
- 2 Most of the time
- 3 A good bit of the time
- 4 Some of the time
- 5 A little of the time
- 6 Hardly any of the time
- 7 None of the time

28. How much of the time during the last two weeks have you been worried about never feeling any better?

- 1 All of the time
- 2 Most of the time
- 3 A good bit of the time
- 4 Some of the time
- 5 A little of the time
- 6 Hardly any of the time
- 7 None of the time
- 29. How much of the time during the last two weeks have you been concerned about the availability of a liver if you need a liver transplant?
- 1 All of the time
- 2 Most of the time
- 3 A good bit of the time
- 4 Some of the time
- 5 A little of the time
- 6 Hardly any of the time
- 7 None of the time

© Younossi 1997 Revised December 28, 1998

Page 73 of 76

ALEXION PHARMACEUTICALS, INC. PROPRIETARY AND CONFIDENTIAL: DO NOT COPY OR DISTRIBUTE WITHOUT PERMISSION

Appendix E: Dose Modification and Stopping Rules for Study LAL-CL04

In the absence of an approved grading scale that can be applied to specific patient populations, this protocol will apply the National Cancer Institute Common Toxicity Classification of Adverse Events (NCI CTCAE), version 4.0 or higher. (http://evs.nci.nih.gov/ftp1/CTCAE/CTCAE_4.03_2010-06-14_QuickReference_8.5x11.pdf).

The following dose modification and stopping rules apply to the decision to pause dosing in individual subjects:

For IARs (refer to the definition in Section 7.1.3), the following stopping rules will apply:

• Subjects who develop a Grade 3 (severe) or higher IAR, defined as significant hypo/hypertension, increased temperature and rigors, significant tachypnea with wheezing and/or stridor, **OR** are IgE or skin test positive must stop treatment until their information is reviewed by the SC. Dosing with alterations to the dose or infusion regimen (e.g., pretreatment and/or slowing the rate of infusion) may resume once the SC and the Sponsor approve. Confirmation may also be sought from regulatory authorities prior to resuming dosing. Subjects with Grade 1 (mild) and/or Grade 2 (moderate) IARs can continue in the study. The SC and/or Sponsor may recommend alterations to the infusion regimen (e.g., pretreatment (e.g., pretreatment and/or slowing the rate of infusion).

 Hypo/hypertension (> 40 mmHg SBP) Respiratory symptoms. Shortness of breath, wheezing, laryngeal edema. Cardiac arrhythmias Anaphylactic/Anaphylactoid shock with hypotension and circulatory collapse. 	 Stop Infusion Give oxygen, if available Give epinephrine IM Give antihistamine IV and consider PO or IV corticosteroids Consider giving a beta- adrenergic inhaler treatment, if appropriate 	 Collect sample for serum tryptase within 1-2 hours of event Obtain serum sample for determination of IgE status at least 3 days after last dose, unless a pre-infusion ADA serum sample was collected Pre-treat with oral antihistamine, antipyretic and corticosteroids prior to (approximately 1.5 hrs) the next infusion Slowly up-titrate the infusion rate during the subsequent infusion e.g., if previous rate was 50 ml/hr, begin at 0.25 x previous rate (12.5 ml/hr) x 15min, then increase to 0.5 x rate (25 ml/hr) x 15min, then increase to 0.75 x rate (37.5 ml/hr) x 15min, then increase to full rate (50 ml/hr) for the remainder of the infusion

If a subject's serum is IgE+ (positive), the subject may continue in the study after the review of his/her data by the Safety Committee and agreement with the Investigator. If a subject's serum is IgE- (negative) and the event was suspected to be immune mediated and was moderate to severe in nature, the subject will be skin tested (according to the Skin Testing guidelines provided in the Study Operations Manual) prior to receiving the next infusion. If results of skin test are negative, the subject may continue in the study. If results of skin test are positive, the subject may only continue in the study after the review of his/her data by the Safety Committee and agreement with the Investigator.

Page 76 of 76

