- a) The infusion should be discontinued.
- b) The subject should be treated for an anaphylactic reaction with intravenous antihistamines, corticosteroids, and epinephrine, if necessary in accordance with institutional standard of care for the subject's age.
- c) Dosing of the patient will be suspended until the Safety Committee has completed review of the IAR, and any other relevant safety data.
- d) Subjects who experience a moderate or severe IAR should have a serum sample collected for tryptase 1 to 3 hours after the IAR onset and another serum sample for tryptase and ADA at least 4 days after the IAR. Skin testing may be considered.

Additional details on the management of subjects with IARs are provided in Appendix F.

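### Appendix F lets a test-negative subject continue after a severe infusion reaction, where Appendix E and section 7.1.3(c) hold dosing for Safety Committee review

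*Protocol*

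**What the plan says.** Three places in the protocol govern what happens after a severe IAR.

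- **Appendix E** gives the stopping rule. It has two triggers joined by OR: an IAR of Grade 3 or higher, or a positive test. Subjects who meet the first, or who "are IgE or skin test positive must stop treatment until their information is reviewed by the SC". Dosing "may resume once the SC and the Sponsor approve". For milder events: "Subjects with Grade 1 (mild) and/or Grade 2 (moderate) IARs can continue in the study".
- **Section 7.1.3, item (c)**, for severe infusion reactions, says: "Dosing of the patient will be suspended until the Safety Committee has completed review of the IAR", together with any other relevant safety data. No test result is mentioned as a condition.
- **Appendix F, closing paragraph**, covers the IgE-negative subject where "the event was suspected to be immune mediated and was moderate to severe in nature". That subject is skin tested "prior to receiving the next infusion". The negative branch reads: "If results of skin test are negative, the subject may continue in the study". On the positive branch, "the subject may only continue in the study after the review of his/her data by the Safety Committee", with the investigator's agreement. An IgE-positive subject also needs SC review.

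Section 7.6 names Appendix E as the place for the stopping rules. Appendix F describes itself as general guidance that does not aim to be complete.

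**The concern.** Appendix F is where section 7.1.3 sends the reader for further detail on managing IARs, so it is likely to be open when a reaction is being handled. For a severe reaction with negative tests it gives a more permissive answer than the stopping rule, and it does not point back to Appendix E or to item (c).

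At stake is a re-infusion after a severe reaction before the SC has looked at it. Long-term safety is the primary objective. Treatment lasts about five years, and infusions may move to local medical centers or, for eligible subjects, to the home. Staff outside the primary centers may therefore rely on the IAR guidance.

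**Working it through.** There is no planned figure to reproduce. The check is a comparison of the texts, case by case.

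**Does the Appendix F paragraph reach Grade 3?** Yes. Its scope runs from moderate to severe, and the table in the same appendix labels severe, life-threatening or anaphylactic reactions as Grade 3 or higher. Only severe is named in the paragraph itself; extending it to the higher grades rests on the table's grouping.

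**Does continuing mean dosing without SC review?** Appendix F does not say so in those words. Three features point that way:

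1. The next sentence allows the skin-test-positive subject to go on only after SC review. The contrast makes the negative branch read as unconditional.
2. The skin test is timed against the next infusion, so the paragraph is about dosing.
3. Appendix E uses almost the same phrase for Grade 1 and 2 subjects, who are not paused.

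**Grid.** Two grades times three test outcomes gives 2 × 3 = 6 cases. A positive test is taken to trigger the Appendix E stop at either grade, as the OR implies. The last outcome is the Appendix F skin-test path for a suspected immune-mediated event.

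| Grade | Test outcome | SC review under Appendix E | SC review stated in Appendix F |
|---|---|---|---|
| 2 | IgE positive | Yes | Yes |
| 2 | IgE negative, skin test positive | Yes | Yes |
| 2 | Both negative | No | No |
| 3 or higher | IgE positive | Yes | Yes |
| 3 or higher | IgE negative, skin test positive | Yes | Yes |
| 3 or higher | Both negative | **Yes** | **No** |

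- Appendix E: 2 (Grade 2) + 3 (Grade 3 or higher) = 5 cases need SC review.
- Appendix F: 2 + 2 = 4 cases.
- Difference: 5 − 4 = 1, the last row. Section 7.1.3(c) sides with Appendix E there.

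The grid counts only whether SC review is required, not who else must agree to a restart.

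**Does the Appendix F table supply the hold?** No. The row for Grade 3 or higher lists four post-reaction activities: a tryptase sample, an IgE sample, pre-treatment before the next infusion, and slow up-titration of the rate. None of the 4 mentions the SC.

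**How many subjects?** Section 4.2 caps enrolment at 9, so the range is 0 to 9. Section 1.5.2 reports no IARs in LAL-CL01, so 0 is possible. That study gave only 4 doses per subject, so it says little about roughly five years of infusions.

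**The case against.** The best reply is that the protocol already answers the question. Appendix E is mandatory, section 7.6 names it as the source of the stopping rules, and item (c) repeats the hold. A reader who reaches Appendix F through section 7.1.3 has just read that item. Appendix F disclaims completeness and never says that SC review may be skipped. Its negative branch can be read as meaning only that the skin test raises no further bar, with the grade-based hold still running. The pre-treatment and slower rate in the Grade 3 or higher row are the kind of changes Appendix E expects once dosing resumes, so that row is compatible with a hold. Other safeguards exist: IARs go to the sponsor within 24 hours, the SC can review ad hoc, and the sponsor or SC may suspend dosing at any time. The Study Operations Manual and SC Charter are not among the documents and may say more.

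Much of this stands. Appendix E takes precedence, the route to harm is narrow, and the Grade 3 or higher row is weak evidence by itself because it describes how the next infusion is given, not when. The objection does not remove the conflict. A disclaimer of completeness excuses an omission; this sentence is an express permission, set against a conditional one in the next sentence. Appendix F also directs investigators to their clinical judgment and not to Appendix E.

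**Conclusion.** The concern holds. For a suspected immune-mediated IAR of Grade 3 or higher with negative IgE and skin tests, Appendix F gives a less safe answer than the protocol's own stopping rule. The conflict is confined to that one case of six; Grade 2 events are unaffected because both appendices let a test-negative Grade 2 subject continue.

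The conclusion rests on two readings: that severe in the closing paragraph corresponds to Grade 3 or higher, as in the Appendix F table, and that permission to continue includes the next infusion. The practical risk is limited to a site that follows Appendix F alone and is not stopped by the sponsor after the 24-hour report. Between 0 and 9 subjects could be affected. No estimate, sample size or analysis depends on this point. It should be corrected, but it does not leave the study without a stopping rule.

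**What to change.** Three wording changes, by amendment or clarification letter:

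1. In the closing paragraph of Appendix F, make the negative-skin-test sentence conditional on the event having been Grade 2.
2. In that paragraph and in the Grade 3 or higher row, add: *After any Grade 3 or higher IAR, whatever the IgE and skin test results, dosing stays on hold until SC review and resumes only with SC and Sponsor approval (Appendix E).* If duplicated rules are a worry, the row can carry a pointer to Appendix E instead.
3. In section 7.1.3(c), add a cross-reference to Appendix E.

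This adds no delay beyond the hold that Appendix E and item (c) already impose, and it has no data or sample-size cost.

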Cmax	The maximum serum level observed over the dose interval	
Cmin	The minimum serum level observed over the dose interval	
CRF	Case Report Form	
CS	Clinically Significant	
CSR	Clinical Study Report	
ECG	Electrocardiogram	
EMA	European Medicines Agency	
ERT	Enzyme Replacement Therapy	
ESR	Erythrocyte Sedimentation Rate	
FACIT	Functional Assessment of Chronic Illness Therapy	
FDA	Food and Drug Administration	
ICH	International Conference on Harmonization	
IMP	Investigational Medicinal Product	
IRR	Infusion Related Reaction	
IAR	Infusion Associated Reaction	
IV	Intravenous	

Z	Apparent terminal rate constant calculated from the regression
	analysis (slope) from the log-transformed measured concentrations on
	the terminal phase of the time-point concentration curve
LAL	Lysosomal acid lipase

Abbreviation Definition

LOQ	Limit of Quantification	
MCS	Mental Component Summary (SF-36)	
MedDRA®	Medical Dictionary for Regulatory	
	Activities	
MEGE	Multi-Echo Gradient Echo	
MEOI	Medical Events of Interest	
NCA	Noncompartment analysis	
PCS	Physical Component Summary (SF-36)	
PD	Pharmacodynamic	
РК	Pharmacokinetic	
PP	Per-Protocol	
PT	Preferred Term	
QOW	Every other week dosing	
QTc	QT-interval for ECG corrected for heart rate	
QW	Once a week dosing	
SAE	Serious Adverse Event	
SAP	Statistical Analysis Plan	
SC	Safety Committee	
SOC	System Organ Class	
SOP	Standard Operating Procedure	
t1⁄2	Apparent terminal half-life	
TEAE	Treatment-Emergent Adverse Event	
tmax	The time to reach the C_{max}	
Vz	Volume of distribution after IV infusion	
WHO	World Health Organization	
WHO-DD	World Health Organization Drug Dictionary	
WNL®	WinNonlin [®]	

1. **OVERVIEW**

This Statistical Analysis Plan (SAP) describes the final planned analysis Protocol LAL-CL04 (An Open Label Multicenter Extension Study to Evaluate the Long-Term Safety, Tolerability, and Efficacy of SBC-102 in Adult Subjects with Liver Dysfunction Due to Lysosomal Acid Lipase Deficiency Who Previously Received Treatment in Study LAL-CL01). The planned analysis identified in this SAP may be included in clinical study reports (CSRs), regulatory submissions, or future manuscripts. Any post hoc, or unplanned, exploratory analysis

In addition to the study protocol and amendments, the following documents were reviewed in preparation of this SAP:

• Case report forms (CRFs) for Protocol LAL-CL04.

performed for the CSR will be clearly identified in the final CSR.

- Clinical Research Protocol LAL-CL01 and associated documents.
- ICH Guidance on Statistical Principles for Clinical Trials (E9).

Readers of this SAP are encouraged to also read the clinical protocol, and other identified documents, for details on the planned conduct of this study. Any statements about patient intervention or trial design are for reader convenience; and are not intended to modify protocol instructions. Operational aspects related to collection and timing of planned clinical assessments are not repeated in this SAP unless relevant to the planned analysis.

